**Draft Protocol v.1.2**

**Principle Investigator:** [name] [name] (CUHK)

**Co-Investigator:** [name], [name], [name], [name], [name], [name], [name]

Protocol Summary	
Design:	Prospective, single-centre, non-randomized, open-label
Target Enrolment:	100 subjects
Study drug:	Empagliflozin 10mg oral tablet daily
Study location	The Chinese University of Hong Kong/ Prince of Wales Hospital.
Study duration	90 days
Inclusion Criteria	

1. Subject age >18 hospitalized for primary diagnosis of acute HF

2. Dyspnoea (exertional or at rest) and 2 of the following signs:

- Congestion on chest X-ray

- Rales on chest auscultation

- Clinically relevant oedema (e.g. <math>\geq 1+</math> on a 0 to 3+ scale)

- Elevated jugular venous pressure

3. Stabilization criteria (while in the hospital):

- SBP <math>\geq 100</math> mmHg and no symptoms of hypotension in preceding 24 hours

- No increase in i.v. diuretic dose for 24 h prior

- No i.v. vasodilators including nitrates within the last 6 h prior

- No i.v. inotropic drugs for 24 h prior

4. NT-proBNP <math>\geq 1600</math> pg/mL or BNP <math>\geq 400</math> pg/mL. Patients with AF: NT-proBNP <math>\geq 2400</math> pg/mL or BNP <math>\geq 600</math> pg/mL. Measured during index hospitalization

5. Heart failure hospitalization that requires the treatment of a minimum single dose of 40 mg of i.v. furosemide (or equivalent i.v. loop diuretics defined as 20 mg of torsemide or 1mg of bumetanide)

Exclusion Criteria	

1. Cardiogenic shock

2. Documented history of HF with previous HF admission

3. Current hospitalization for acute HF primarily triggered by pulmonary embolism, cerebrovascular accident, or acute MI

4. Interventions in past 30 days prior or planned during the study:

- Major cardiac surgery, or Tran Aortic Valve Implantation, or Percutaneous Coronary Intervention, or MitraClip

- Implantation of cardiac resynchronization therapy device

- Cardiac mechanical support implantation

4. Current or expected heart transplant, LVAD, IABP, or patients with planned inotropic support in an outpatient setting

5. Haemodynamically severe uncorrected primary cardiac valvular disease planned for surgery or intervention during the course of the study.

6. eGFR <math>< 20</math> mL/min/1.73m^2 as measured during index hospitalization (latest measurement before randomization) or patients requiring dialysis

7. Type 1 diabetes mellitus

8. History of ketoacidosis, including diabetic ketoacidosis

	9. Current or prior treatment with SGLT2 inhibitors in 90 days prior to enrolment
Primary Clinical Outcome	Clinical benefit, a composite of all cause mortality, number of heart failure events (including hospitalization for HFs, urgent heart failure visits and unplanned outpatient visits), time to first heart failure event, change from baseline in 6-minute walk distance (6MWD) and change from baseline in KCCQ-TSS after 90 days of treatment.
Secondary Outcomes	
 
• Change from baseline in KCCQ-TSS after 90 days of treatment.
 
• Change from baseline in log-transformed NT-proBNP level over 90 days of treatment.
 
• Change in NYHA class
 
• Days alive and out of hospital from study drug initiation until 90 days after initial hospital discharge.
 
• Days alive and out of hospital from study drug initiation until 90 days after randomization.
 
• Time to first occurrence of cardiovascular death or heart failure event until end of trial visit.
 
• Occurrence of HHF until 90 days after initial hospital discharge.
 
• Occurrence of chronic dialysis or renal transplant or sustained reduction of <math>\geq 40\%</math> eGFR, or 
 
- Sustained eGFR <math>< 15\text{mL/min}/1.73\text{m}^2</math> for patients with baseline eGFR <math>\geq 30\text{ mL/min}/1.73\text{m}^2</math>
 
- Sustained eGFR <math>< 10\text{mL/min}/1.73\text{m}^2</math> for patients with baseline eGFR <math>< 30\text{ mL/min}/1.73\text{m}^2</math>.
 
 
 
• Weight loss per mean daily loop diuretic dose after 15, 30, 60 and 90 days of treatment.
 
• Change from baseline in 6MWD at 90 days.
 
• Cost effectiveness of early initiation of empagliflozin for heart failure events avoided and quality-of-life years (QALY) gained.
 

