The EMPULSE study which was recently presented at the 2021 American Heart Association Annual scientific session, demonstrated in-hospital initiation of empagliflozin in patients with acute heart failure regardless of left ventricular ejection fraction (LVEF) to be safe and effective (10). In this trial, 530 patients with acute HF were randomized 1:1 to 10 mg of empagliflozin or placebo once stabilized in the hospital (median 3 days) and followed-up for 90 days for the primary composite endpoint of time to death, frequency of HF events, time to first HF event, and change in quality of life score from baseline. About one-third (33%) patients randomized had new-onset acute HF, two-thirds (69.1%) of patients had LVEFs <40%, and 29% randomized to empagliflozin and 35% of those randomized to placebo had LVEF >40%. In terms of safety, rates of serious adverse events and any adverse events were both higher in the placebo arm. Acute renal failure, occurred in 7.7% of patients in the SGLT2 inhibitor arm compared with 12.1% of placebo-treated patients. For the primary composite endpoint, patients treated with empagliflozin were 36% more likely to experience a clinical benefit in the first 90 days (stratified win ratio 1.36; 95% CI 1.09-1.68). all-cause mortality (4.2% vs 8.3%) and heart failure events (10.6% vs 14.7%) were numerically lower in the empagliflozin arm. Improvement in quality of life was a key driver of difference in the primary endpoint: placebo-adjusted mean difference at 90 days was 4.5 points favouring empagliflozin. Other larger trials of treatment with SGLT2 inhibitor in acute heart HF are underway, including the DICTATE-AHF and DAPA ACT HF-TIMI 68 trials, both with dapagliflozin.

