**Study Endpoints:**

The primary outcome is clinical benefit at 90 days defined as a composite of all cause mortality, number of heart failure events (including hospitalization for HFs, urgent heart failure visits and unplanned outpatient visits), time to first heart failure event and change in KCCQ-TSS from baseline.

Secondary outcomes include improvement in KCCQ-TSS of  $\geq 10$  points after 90 days of treatment, change from baseline in log-transformed NT-proBNP levels over 90 days, days alive and out of hospital until 90 days, time to first occurrence of CV death or HFE until end of trial period, and change in 6-minute walk test and change in KCCQ-TSS between baseline and 90 days. Secondary safety endpoints include Occurrence of chronic dialysis or renal transplant or sustained reduction of  $\geq 40\%$  eGFR, or Sustained eGFR  $< 15\text{mL/min}/1.73\text{m}^2$  for patients with baseline eGFR  $\geq 30\text{mL/min}/1.73\text{m}^2$ , or Sustained eGFR  $< 10\text{mL/min}/1.73\text{m}^2$  for patients with baseline eGFR  $< 30\text{mL/min}/1.73\text{m}^2$ .

**Statistical analysis:** Categorical variables will be reported as percentages and counts, and continuous variables will be reported as means  $\pm$  standard deviations. Data analysis will be performed using STATA version 15 software (College Station, TX, USA).

Cost-effectiveness analysis will be performed to calculate incremental-cost effective ratio (ICER) for HFE avoided and QALY gained. Events of patients enrolled in the registry will be used as reference comparator. Costs will be based on Hospital Authority gazette prices for hospital admissions and visits.

*Table 1. Data to be collected in this study*

	Enrollment	30 days	60 days	90 days
Patient Informed Consent	x			
History including baseline characteristics	x			
Baseline co-morbidities:	x			

Baseline and in-hospital medications	x			
Physical examination include body weight	x	x	x	x
Laboratory test including NT-proBNP or BNP within 72hr of index admission, eGFR	x	x	x	x
Clinical events: all cause mortality, cardiovascular-associated death, A&E visit for acute heart failure, unplanned outpatient clinic visit, re-admission for heart failure	x	x	x	x
6MWD	x			x
Symptoms QOL assessment: NYHA class, KCCQ-TSS	x			x
Prescription records of SGLT2 inhibitors	x	x	x	x
Adverse drug effects	x	x	x	x

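### The primary composite includes change in 6-minute walk distance in the Protocol Summary but not in the Methods, and nothing says which definition governs

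*Protocol*

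**What the plan says.** **Protocol Summary, Primary Clinical Outcome.** Clinical benefit is a composite of death from any cause, the count of heart failure events, the time to the first such event, and then "change from baseline in 6-minute walk distance (6MWD) and change from baseline in KCCQ-TSS after 90 days of treatment". That is five components.

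**Section 2 (Methods), Study Endpoints.** "The primary outcome is clinical benefit at 90 days defined as a composite of all cause mortality", followed by the count of heart failure events, and closing with "time to first heart failure event and change in KCCQ-TSS from baseline". That is four components, without walk distance.

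**Secondary outcomes.** The Summary lists "Change from baseline in 6MWD at 90 days" and also lists change in KCCQ-TSS separately. The Methods list "change in 6-minute walk test and change in KCCQ-TSS between baseline and 90 days".

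**Section 1 (Introduction).** The cited placebo-controlled trial of in-hospital empagliflozin is described as having a "composite endpoint of time to death, frequency of HF events, time to first HF event, and change in quality of life score from baseline". That is a four-item form without walk distance. The protocol does not say that this trial's definition governs the present study.

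**Design.** The Summary gives it as "Prospective, single-centre, non-randomized, open-label".

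**The concern.** The label and the 90-day time point are the same in both places, but the component lists differ. Neither text is an amendment log. The difference is not one of abbreviation either: a summary may shorten the body, but here the Summary contains a component that the body lacks.

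Adding a continuous component can change the result of a composite. While both definitions stand, either could be reported as the protocol's primary outcome. Treatment is open-label, so results can be seen by group as they accrue, and the choice could follow the data. A statistical analysis plan cannot cure this, because any single definition it adopted would contradict one of the two protocol texts.

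**Working it through.** **Step 1. Compare the components.**

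| Component | Summary | Methods |
|---|---|---|
| Death from any cause | yes | yes |
| Number of heart failure events | yes | yes |
| Time to first heart failure event | yes | yes |
| Change in 6MWD | yes | no |
| Change in KCCQ-TSS | yes | yes |
| Total | 5 | 4 |

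Only 6MWD differs.

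**Step 2. Does the secondary listing settle it?** No. Change in 6MWD is secondary in both places, but so is change in KCCQ-TSS, which sits in both primary composites. Being listed as secondary therefore does not exclude a variable from the primary in this protocol.

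**Step 3. Does any other text settle it?** No statement gives the Summary or the Methods precedence. The description of the cited trial matches the Methods list, which suggests where that list came from but is not a rule.

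**Step 4. Can both versions be computed?** Yes. Table 1 schedules 6MWD and KCCQ-TSS at enrolment and at 90 days.

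**Step 5. Illustration of how much could turn on 6MWD.** The protocol gives no figure to reproduce. This step assumes a two-group pairwise comparison (win ratio) in the listed order, which the protocol does not state for its own composite. The event rates are those quoted in the Introduction for the cited trial: deaths 4.2% vs 8.3%, heart failure events 10.6% vs 14.7%. Any pair with at least one death or heart failure event is taken as settled before the continuous components.

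- Not settled by death: (1 − 0.042)(1 − 0.083) = 0.878.
- Not settled by a heart failure event: (1 − 0.106)(1 − 0.147) = 0.763.
- Reaching the continuous components, if death and heart failure events are independent: 0.878 × 0.763 = 0.670.

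Sensitivity to the event rates:
- All four rates halved: 0.979 × 0.9585 × 0.947 × 0.9265 = 0.823.
- All four rates × 1.5: 0.937 × 0.8755 × 0.841 × 0.7795 = 0.538.

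Sensitivity to the overlap of deaths and heart failure events:
- No overlap: 4.2% + 10.6% = 14.8% and 8.3% + 14.7% = 23.0%, so (1 − 0.148)(1 − 0.230) = 0.66.
- All deaths among patients with heart failure events: (1 − 0.106)(1 − 0.147) = 0.76.

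Under the Methods list, KCCQ-TSS alone decides these pairs. Under the Summary list, 6MWD comes first. With no minimum difference for a win, 6MWD decides nearly all of them. With an assumed 30 m minimum, normally distributed changes, equal means and an assumed SD of the change, P(tie) = 2Φ(30 / (SD√2)) − 1:

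| Assumed SD (m) | P(tie on 6MWD) | Decided by 6MWD, share of all pairs: 0.670 × (1 − P) | Left for KCCQ-TSS, at most: 0.670 × P |
|---|---|---|---|
| 60 | 0.276 | 0.485 | 0.185 |
| 80 | 0.209 | 0.530 | 0.140 |
| 100 | 0.168 | 0.557 | 0.113 |

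**The case against.** The contradiction itself is hard to dispute. The case on the other side concerns framing and weight.

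- **One outcome, not two.** The protocol names one primary outcome and gives it two component lists that share four items. This stands: the fault is two conflicting definitions of one outcome.
- **The illustration describes an analysis the protocol does not contain.** The statistical paragraph gives descriptive summaries only, and it names the registry of patients who declined the drug as comparator only for cost-effectiveness. Without a two-group comparison there are no pairs. The hierarchy, its order, the 30 m margin and the SDs are also assumed, and the rates come from a trial in which about one-third of patients had new-onset heart failure. This stands too, so the percentages are hypothetical and the finding must rest on the component count.
- **Differing from the cited trial is no error.** This is correct, since the protocol never undertakes to reproduce that composite. The match bears only on which edit is simplest.
- **Non-randomisation adds nothing to the worry about post-hoc choice.** This is fair. The argument rests on two live definitions and open-label access to results.
- **No data are lost and the edit is small.** This is true, but it shows that the repair is cheap rather than unnecessary. The primary result stays undefined until the repair is made.

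**Conclusion.** The concern holds. The protocol defines its primary outcome in two incompatible ways, five components in the Summary and four in the Methods, and no text resolves the conflict. That much is certain and rests on no assumption.

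How far the result could depend on the choice is conditional. With a win ratio in the listed order and the cited trial's rates, about 67% of pairs would reach the continuous components. The range is 54% to 82% when event rates are 1.5 times or half those quoted, and 66% to 76% across the two extremes of overlap between deaths and heart failure events. With the assumed 30 m margin and SDs of 60 to 100 m, 6MWD would decide about 49% to 56% of all pairs under the Summary definition and none under the Methods definition. No effect on the study's conclusion is claimed. Because the primary outcome itself is affected, this must be corrected.

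**What to change.** Before any outcome data are analysed, state one primary composite in identical terms in the Summary and in Study Endpoints, and say explicitly whether change in 6MWD is a component or a secondary outcome only.

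- **Simplest route:** keep the four-component Methods list and delete the 6MWD item from the Summary's primary outcome. This matches the cited trial's composite, and 6MWD is still reported as secondary.
- **Alternative:** if the sponsor intends 6MWD as a component, add it to the Methods definition and describe its separate secondary listing as a component analysis.

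The choice is the sponsor's. Either route costs one short text amendment. No additional patients, visits or measurements are needed, because Table 1 already collects both variables at enrolment and 90 days.

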## 1. Introduction

Heart failure (HF) is one of the most important reasons for hospital admission and is associated with high mortality and morbidity (1). After discharge, up to 40% of patients are readmitted within 6 months and 1-year post-discharge mortality is high (2-4). The cost burden of treating patients with HF is high and  $\sim 80\%$  of healthcare costs are related to hospital admissions (5).

Sodium-glucose cotransporter-2 (SGLT2) inhibitor is considered one of the four foundational therapies (ACE-I or ARNI, beta-blockers, MRA, and SGLT2 inhibitors) for HFrEF (6). However, guidelines do not specify the sequence and the timing of which therapy to be commenced. In particular, empagliflozin has been shown in randomized controlled trials to reduce the combined risk of cardiovascular death or HF hospitalization in HF patients with both reduced ejection fraction (HFrEF) and preserved ejection fraction (HFpEF), respectively, regardless of the presence or absence of diabetes in the EMPEROR-Reduced and EMPEROR-Preserved trials (7, 8). Empagliflozin is the first medical therapy with proven benefits for patients with HFpEF which accounts for approximately 50% of heart failure cases in Hong Kong (9). In September 2021, the FDA granted breakthrough therapy designation for empagliflozin as an investigational treatment for adults with HFpEF. Furthermore,

the benefits of empagliflozin are seen early in the treatment course, and is maintained during subsequent follow-ups.

The EMPULSE study which was recently presented at the 2021 American Heart Association Annual scientific session, demonstrated in-hospital initiation of empagliflozin in patients with acute heart failure regardless of left ventricular ejection fraction (LVEF) to be safe and effective (10). In this trial, 530 patients with acute HF were randomized 1:1 to 10 mg of empagliflozin or placebo once stabilized in the hospital (median 3 days) and followed-up for 90 days for the primary composite endpoint of time to death, frequency of HF events, time to first HF event, and change in quality of life score from baseline. About one-third (33%) patients randomized had new-onset acute HF, two-thirds (69.1%) of patients had LVEFs <40%, and 29% randomized to empagliflozin and 35% of those randomized to placebo had LVEF >40%. In terms of safety, rates of serious adverse events and any adverse events were both higher in the placebo arm. Acute renal failure, occurred in 7.7% of patients in the SGLT2 inhibitor arm compared with 12.1% of placebo-treated patients. For the primary composite endpoint, patients treated with empagliflozin were 36% more likely to experience a clinical benefit in the first 90 days (stratified win ratio 1.36; 95% CI 1.09-1.68). all-cause mortality (4.2% vs 8.3%) and heart failure events (10.6% vs 14.7%) were numerically lower in the empagliflozin arm. Improvement in quality of life was a key driver of difference in the primary endpoint: placebo-adjusted mean difference at 90 days was 4.5 points favouring empagliflozin. Other larger trials of treatment with SGLT2 inhibitor in acute heart HF are underway, including the DICTATE-AHF and DAPA ACT HF-TIMI 68 trials, both with dapagliflozin.

Current guidelines recommend in-hospital echocardiogram in the clinical setting of new-onset or decompensated (6). However, echocardiogram is often delayed months after discharge or not performed at all under Hong Kong public hospital setting. As a result, initiation of guideline recommended therapies like ARB/ARNI/MRA/BB may be delayed for HFrEF patients awaiting echocardiogram or unnecessary for HFpEF patients. Out of the 4 guidelines recommended treatment for HF, only empagliflozin has proven benefits for the treatment of both HFrEF and HFpEF. Given that empagliflozin is well tolerated and its benefits are seen early, it may be reasonable to initiate empagliflozin early during index hospitalization even before the assessment of LVEF is available. However, costs remains a major barrier for early initiation of SGLT2-inhibitor.

The timing of SGLT inhibitors initiation in the treatment of acute HF is not established. In particular, new-onset acute HF is a group which is understudied in the major trials to date. This study aims to evaluate the efficacy and safety of in-hospital initiation of empagliflozin in patients hospitalized for new onset acute HF, regardless of LVEF for up to 90 days of follow-up.

## 2. Methods

**Study design:** This is an investigator-initiated, prospective, single-centre, non-randomized open label study that evaluates the efficacy and safety of initiating empagliflozin during index hospitalization for acute heart failure regardless of LVEF.

**Patient population:** The study will recruit up to 200 patients.

### Inclusion criteria:

1. Subject age >18 hospitalized for primary diagnosis of acute HF
2. Dyspnoea (exertional or at rest) and 2 of the following signs:
  - Congestion on chest X-ray

- Rales on chest auscultation
- Clinically relevant oedema (e.g.  $\geq 1+$  on a 0 to 3+ scale)
- Elevated jugular venous pressure

3. Stabilization criteria (while in the hospital):

- SBP  $\geq 100$  mmHg and no symptoms of hypotension in the preceding 24 hours
- No increase in i.v. diuretic dose for 24 h prior
- No i.v. vasodilators including nitrates within the last 24 h prior
- No i.v. inotropic drugs for 24 h prior

4. NT-proBNP  $\geq 1600$  pg/mL or BNP  $\geq 400$  pg/mL. (Patients with AF: NT-proBNP  $\geq 2400$  pg/mL or BNP  $\geq 600$  pg/mL. Measured during index hospitalization

5. Heart failure hospitalization that requires the treatment of a minimum single dose of 40 mg of i.v. furosemide( or Equivalent i.v loop diurectics defined as 20 mg of torsemind or 1mg of bumetanide)

**Exclusion criteria:**

1. Cardiogenic shock
2. Documented history of HF with previous HF admission
2. Current hospitalization for acute HF primarily triggered by pulmonary embolism, cerebrovascular accident, or acute MI
3. Interventions in the past 30 days prior or planned during the study:
  - Major cardiac surgery, or TAVI, or PCI, or MitraClip
  - Implantation of cardiac resynchronization therapy device
  - Cardiac mechanical support implantation
4. Current or expected heart transplant, LVAD, IABP, or patients with planned inotropic support in an outpatient setting
5. Haemodynamically severe uncorrected primary cardiac valvular disease planned for surgery or intervention during the course of the study
6. eGFR  $< 20$  mL/min/1.73m^2 as measured during index hospitalization (latest measurement before randomization) or patients requiring dialysis
7. Type 1 diabetes mellitus
8. History of ketoacidosis, including diabetic ketoacidosis
9. Current or prior treatment with SGLT2 inhibitors in the 90 days prior to enrolment.

**Study locations:** This study will be primarily conducted at The Chinese University of Hong Kong/ Prince of Wales Hospital.

**The study drug:**

Empagliflozin 10mg daily (open label)

**Study procedure:**

Patients who meet inclusion and none of the exclusion criteria will be enrolled during hospitalization after stabilization. Patients should receive usual care per current relevant local and regional guidelines, as defined by their clinicians. Patients can be enrolled regardless of T2D status or ejection fraction. Enrolment is stratified according to patients with new-onset HF and worsening chronic HF. Informed consent will be signed before study enrolment. Baseline KCCQ-TSS and baseline 6MWT will be performed prior to study drug initiation and repeated at 30 and 90 days. Echocardiogram is not mandatory but permitted before subjects enrolment. Follow-up will be at 30 days, 60 days and 90 days.

Study drug will be dispensed by the research pharmacy provided by the study team (free of charge to the patient) as an open-label treatment.

Patients who meet inclusion and none of the exclusion criteria but declined study medication will be invited to be followed-up in a registry as reference group. These patients will follow the same baseline and follow-up assessment protocol (minus the study drug).

